## REVISION HISTORY

Revision #	Version Date	Summary of Changes	Consent Change?
1	July 29, 2020	Minor edits to web survey text, change in data storage plan for web survey data, per HIPCO	No
2	November 30, 2020	Edits to the plan for the PDMP data acquisition, storage, and analysis.	
3	December 8, 2020	Revised interim outcomes analysis plan approved by Data Monitoring Committee, and uploading the approved Data Monitoring Committee charter.	No
4	February 24, 2021	Including report from Data Monitoring Committee and changes to protocol to reflect those recommendations.	No
5	May 9, 2022	Minor changes to the analysis plan that were made before starting the actual data analysis	No

## **ABBREVIATIONS/DEFINITIONS**

- CDC: Centers for Disease Control and Prevention
- QI: Quality Improvement
- EHR: Electronic Health Record
- (1)ICS: Informatics Consulting Services
- MMB: Minnesota Management and Budget
- MME: Morphine Milligram Equivalent
- PCP: Primary Care Provider
- PDMP: prescription drug monitoring program
- PMP: Prescription Drug Monitoring Program
- MMB: Minnesota Management and Budget
- UMP: University of Minnesota Physicians
- DEA: Drug Enforcement Agency

## 1.0 Objectives

### 1.1 Purpose:

The objective of this research is to assess the effects of EHR-based decision support tools on primary care clinician decisionmaking around pain treatment and opioid prescribing. EHR-based clinical decision support tools are a common feature of QI. The decision support tools are informed by principles of “behavioral economics,” whereby clinicians are “nudged,” though never forced, towards guideline-concordant care.

To test the effects of these decision support tools for improving the quality of care for pain treatment, we will implement a clinic-randomized QI study across the primary care clinics of Fairview Medical Group and University of Minnesota Physicians.

The study has two parallel components. The decision support tools to be tested will differ somewhat depending on whether a given patient is opioid-naïve, or whether a given patient is a current opioid-user. Four sets of analyses will be conducted separately: one for the opioid-naïve group using EHR data, one for the current opioid-user group using EHR data, one at the PCP-level using web survey data, and one at the PCP-level using MN Prescription Drug Monitoring Program data.

## 2.0 Background

### 2.1 Significance of Research Question/Purpose:

Three of the key dimensions to addressing the current opioid crisis are a) how to minimize the number of patients who are starting opioids and therefore at risk of developing dependence, b) ensuring that opioids that are prescribed are prescribed appropriately and safely, and c) how to effectively and safely reduce prescription opioid use among current users of prescription opioids.

Prior research establishes that behavioral economics-informed interventions that are embedded within the EHR can successfully improve clinicians’ decisionmaking. For example, an influential paper by Meeker and colleagues (1), showed that EHR-based “nudges,” similar to what we propose to test, successfully reduced rates of inappropriate antibiotic prescribing. A few studies use quasi-experimental methods to examine how changes in the EHR infrastructure affect opioid prescribing decisions, with mixed results.

As the opioid crisis continues, there is an urgent need to develop effective methods for improving pain treatment and opioid prescribing in primary care. Behavioral economics-informed interventions may be especially useful in the context of pain treatment and opioid prescribing. Specifically, decisions about opioid versus non-opioid treatments, monitoring opioid use, initial prescribing, and decisions around tapering and/or discontinuing opioids are idiosyncratic to the patient. Therefore, interventions which nudge towards treatment guidelines, without compelling any clinical action, may be especially promising.

We are proposing to implement a primary care clinic-randomized study of two sets of behavioral economics-informed interventions embedded in the EHR, to improve pain treatment and opioid prescribing decisions.

## 2.2 Preliminary Data:

We recruited five clinicians to pilot-test the interventions, and one additional PCP from the PRINCE study team ([name]) also pilot-tested the interventions. The pilot testers included a mix of three PCPs and three pain clinicians. The pilot-testing took place from 11/27/18 to 12/25/18. We received extensive feedback in the semi-structured exit interviews about how to improve the usability of the interventions, which informed the modifications we subsequently made to the interventions

## 2.3 Existing Literature:

There is a recent and growing literature that studies how EHR-based “nudges” can affect clinician behavior around opioid prescribing and pain treatment. For example, two recent studies found that reducing the default number of pills per opioid prescription order within the EHR led to reduced amount of opioids prescribed after surgical procedures and at emergency department discharge (2, 3). However, other research on nudges to improve opioid prescribing found that introducing safety alerts in the EHR for when a patient was being co-prescribed an opioid and a benzodiazepine was not associated with changes in prescribing patterns (4). Overall, there are many open questions about the types of EHR-based alerts and reminders can effectively improve opioid prescribing patterns and pain treatment decisions.

Another important component of safe and appropriate opioid prescribing is the CDC guideline recommendation to check the PDMP to identify potentially problematic patterns of opioid use. A number of studies examine the effects of laws that mandate providers to check their state’s PDMP on prescribing patterns and on opioid use patterns (5). Other research notes that many providers do not check the PDMP when prescribing opioids, or do so relatively infrequently (6-8). Reasons for the underuse of PDMPs by prescribers include that the data in the PDMP are difficult and time-consuming to access (7, 8). One approach to “nudge” providers to use the PDMP more frequently and effectively is to simply make it much easier to use, by integrating it directly into a patient’s EHR. Very limited evidence to date exists on the effects of PDMP integration into the EHR (9). We are not aware of any randomized trials of PDMP integration into the EHR.

## 3.0 Study Endpoints/Events/Outcomes

### 3.1 Primary Endpoint/Event/Outcome:

**Opioid-Naïve Population:** Whether or not an opioid is prescribed in a primary care visit, *without* currently receiving a non-opioid alternative pain treatment (including a new order for a non-opioid pain treatment).

**Current Opioid-User Population:** A variable with three mutually-exclusive categories:

Category 1 (appropriate taper): Whether a primary care appointment with someone currently receiving a “high risk” opioid had an order that would reduce MME by no greater than 20%, relative to the current prescription, and there is documented evidence that the reduction was consistent with CDC guidelines. “High risk,” is defined as a patient is currently receiving opioids with >50 MME and/or currently receiving both an opioid and a benzodiazepine.

Category 2 (“inappropriate” taper): Whether a primary care appointment with someone currently receiving a “high risk” opioid had an order that would reduce MME without documented evidence that the reduction was consistent with CDC guidelines, or, decreased MME by greater amounts than recommended (>20% relative reduction in MME).

Category 3 (no taper): Whether a primary care appointment with someone currently receiving a “high risk” opioid had no reduction in MME.

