### 3.2 Secondary Endpoint(s)/Event(s)/Outcome(s):

#### Opioid-Naïve Population:

- 1) Whether a CDC-recommended non-opioid treatment is ordered in a primary care visit (e.g., referral to physical therapy, prescription of an NSAID, referral to pain clinic)
- 2) The length of opioid prescriptions
- 3) The MME of opioid prescriptions

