## 4.0 Study Intervention(s)/Interaction(s)

### 4.1 Description:

The subjects of the study are primary care clinicians working in Fairview and in University of Minnesota Physicians. The interventions to be tested in this study are

sets of EHR clinical decision support tools (some of which are referred to as, “Best Practice Alerts”). These tools are very similar to many other EHR tools and alerts that clinicians encounter and use in their practice, and which are frequently adopted by health systems.

[figure not shown]
There are two sets of interventions to be tested. Both of these intervention sets use behavioral economics principles around “choice architecture.” One set includes a pair of EHR alerts – one that triggers for patients who are opioid-naïve (i.e., have not had an active opioid prescription in the past six months), and one that triggers for patients who are current opioid users. The other intervention is essentially the same for patients who are opioid-naïve or current opioid users.

These interventions will be delivered to all of the PCPs working in Fairview and UMP primary care clinics that are assigned to one of the intervention arms of the study (randomization arms are described in Section 5).

Detailed description of the Intervention Set A (choice architecture):

For the opioid-naïve group, the interventions will “fire” when a PCP initiates an opioid order within the EHR for a patient who has not had an opioid prescription within the past six months. The alert, shown in Exhibit 1a, provides guidance language about opioid prescribing and prompts the PCP to open the “SmartSet” to order non-opioid treatment alternatives. PCPs can choose to ignore this, but opening the SmartSet is the default option. When the SmartSet is opened, PCPs can choose to click on a variety of treatment order options, including both non-opioid pharmacological options and non-pharmacological options (e.g., referral to physical therapy or pain clinic). Clicking on a category expands the selections, and Exhibit 1b shows the SmartSet with the non-pharmacologic options expanded. The non-opioid treatment options were selected for the intervention based on the CDC’s chronic pain recommendations and the Fairview Opioid Network Team’s recommendations.

Exhibit 1a.

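### A better result on the opioid-naive primary endpoint cannot by itself show fewer opioid starts, because no listed outcome records whether an opioid was ordered at the visit

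*Combined protocol and SAP*

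**What the plan says.** The opioid-naive primary outcome in Section 3.1 begins "Whether or not an opioid is prescribed in a primary care visit". It counts the visit as an event if an opioid is prescribed and the patient is not "currently receiving a non-opioid alternative pain treatment (including a new order for a non-opioid pain treatment"). The interim plan in Section 17.1 repeats this definition and bases the interim decision on the opioid-naive population only.

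Section 3.2 lists three opioid-naive secondary outcomes: "Whether a CDC-recommended non-opioid treatment is ordered in a primary care visit", "The length of opioid prescriptions" and "The MME of opioid prescriptions". The same three go to the Data Monitoring Committee. The outcomes for all PCPs are PMP checks and satisfaction, and the exploratory outcome concerns high-risk users who were not tapered. Section 5.3 mentions longer-term prescribing patterns but defines no outcome for them.

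Section 4.1 says the Set A alert for opioid-naive patients fires when an opioid order is initiated, gives guidance language, and leads to a SmartSet of non-opioid orders: "PCPs can choose to ignore this, but opening the SmartSet is the default option".

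Section 2.1 names, among three key dimensions of the opioid crisis, "how to minimize the number of patients who are starting opioids and therefore at risk of developing dependence". Section 17.2 states the difference of clinical interest, and Exhibit 8 the power, in terms of the share of eligible visits at which an opioid is prescribed, with no reference to co-treatment.

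**The concern.** A visit leaves the event category either because the opioid was avoided or because a non-opioid pain treatment was ordered alongside it. Both may be desirable, but they are different findings. The first means fewer patients exposed. The second leaves exposure as it was.

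Set A prompts the second route at the moment when an opioid order is already under way. A benefit on the primary endpoint in the Set A comparison could therefore come wholly from added orders. The quantity that Section 17.2 treats as clinically interesting, any opioid prescribed, is not a listed opioid-naive outcome. The final report would then have no planned comparison with which to say whether opioid starts changed.

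**Working it through.** **1. The plan's own figure.** Inputs from Exhibit 8 and Section 17.2: control rate 7%; 48 clinics in four equal arms, so 12 per arm; 10 providers per clinic; 30 or 15 eligible visits per provider per month; months 1-6; two-sided 0.05. Section 17.3 adds 12 pre-intervention months. Exhibit 8 states no formula. A log-odds difference-in-differences, with the random intercepts assumed to cancel, reproduces it:

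power = Φ(|logit p1 − logit p0| / √V − 1.96), V = 2/[n_post p0(1−p0)] + 2/[n_pre p0(1−p0)].

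At 30 visits, n_post = 12 × 10 × 30 × 6 = 21,600 and n_pre = 43,200. For a 15% reduction p1 = 5.95%, the logit difference is 0.174, V = 2/1,406 + 2/2,812 = 0.00213 and √V = 0.0462. Power is Φ(3.76 − 1.96) = 96.4%, against 96% stated. For reductions of 15/20/25/30% the formula gives 96.4/99.9/100/100% at 30 visits (stated 96/100/100/100%) and 75.8/95.4/99.7/100% at 15 visits (stated 76/95/100/100%). The formula is inferred, and some variants with a 5% control rate also match. What matters here is that the powered quantity is any opioid prescribed, not the Section 3.1 outcome.

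**2. What moves the primary endpoint.** Let S be the share of eligible visits with an opioid and c the share of those that also have a non-opioid. The event rate is E = S(1 − c). If a fraction u of the opioid orders that would otherwise stand alone gain a non-opioid, and S does not change, then E′ = S(1 − c)(1 − u) and E′/E = 1 − u. Both S and c cancel. The documents give neither c nor u; the ranges below are assumptions. With S fixed at 7%:

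| c before | E before | u = 15%: c after, E after | u = 30%: c after, E after |
|---|---|---|---|
| 0% | 7.00% | 15.0%, 5.95% | 30%, 4.90% |
| 30% | 4.90% | 40.5%, 4.17% | 51%, 3.43% |
| 50% | 3.50% | 57.5%, 2.98% | 65%, 2.45% |

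No opioid start is averted in any cell. Section 17.2's text uses 5% where Exhibit 8 uses 7%; at S = 5% and c = 50%, u = 30% takes E from 2.50% to 1.75%. The endpoint can even improve while starts rise: S from 7.0% to 7.7% with c from 30% to 50% takes E from 4.90% to 3.85%, a 21% relative fall.

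**3. Whether the listed outcomes separate the routes.** Take 10,000 eligible visits with 500 opioid orders, 250 of them without a non-opioid, and let 75 of those 250 change.

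| | Added to the opioid | Replaces the opioid |
|---|---|---|
| Primary events | 250 → 175 | 250 → 175 |
| Extra visits with a non-opioid ordered | 75 | 75 |
| Visits with an opioid | 500 → 500 | 500 → 425 |

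The primary outcome and the first secondary outcome are identical in the two columns. Length and MME are described for opioid prescriptions, with no rule for visits without one, so they need not differ either. Only the unlisted last row tells the columns apart.

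**4. Whether such a change would be detected.** Using the design of step 1 with arm-specific variances and S unchanged at 7%, the chance of a significant primary benefit at u = 15% is 96%, 86% and 72% for c = 0, 30 and 50% at 30 visits, and 74%, 57% and 44% at 15 visits. At u = 30% it is about 97% to 100% in all six cases. A test on opioid starts would reject at its 5% error rate. These figures compare one arm with control at 0.05, as in step 1. The pooling of arms in Section 17.3 would raise them, and its Bonferroni correction would lower them.

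**The case against.** The endpoint is defined openly and fits the stated objective. Section 1.1 concerns decision-making and guideline-concordant care, and Section 2.1 also lists appropriate and safe prescribing, which an opioid-without-alternative measure reflects well. That stands, and it is why the primary endpoint should be kept.

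Several stronger readings are tempting and are not supported:

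- That reducing starts is the study's first aim. Section 2.1 lists it as a dimension of the crisis, in the background.
- That Set A works only by adding orders. Section 4.1 also describes guidance language about opioid prescribing, so Set A may act on both routes.
- That the same prompt applies to Set B. PMP access and its reminder do not prompt non-opioid orders.
- That a single click is enough. Sections 4.1 and Exhibit 1b describe opening the SmartSet, expanding a category and choosing an order.
- That the committee or readers will be misled. No section says a positive result will be reported as fewer starts, and the committee does see non-opioid ordering.

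The listed outcomes are also partly informative. If the primary rate fell with no rise in non-opioid orders, added new orders would be an unlikely explanation. Section 17.3 plans descriptive statistics by arm, and the prescription data behind length and MME would let opioid orders be counted. This narrows the gap. It does not close it, because replacement and addition both raise non-opioid ordering and no comparison of opioid starts is prespecified.

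**Conclusion.** The point holds as a limit on interpretation, most directly for Set A. A positive opioid-naive result is compatible with fewer opioid starts but cannot show them, and the planned outcomes do not formally separate the two routes. In size, adding a non-opioid to 15% to 30% of opioid orders that would otherwise have none lowers the primary event rate by the same 15% to 30% in relative terms, with no change in starts. The uptake is an assumption; the equality holds for any baseline co-treatment share. The detection figures rest also on an inferred power formula and on assumed co-treatment shares, and the conclusion does not depend on them. A reader might infer that the primary endpoint is invalid or that the trial cannot inform prescribing quality. The documents do not support either.

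**What to change.** Keep the primary endpoint and make three additions.

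1. In Section 3.2, add any opioid ordered at the visit (yes/no, over all eligible opioid-naive visits) as a secondary outcome, analysed with the mixed logistic model of Section 17.3.
2. Report by arm the shares of eligible visits with no opioid, with an opioid and a non-opioid, and with an opioid alone.
3. State that a claim of reduced opioid initiation requires an effect on any opioid ordered.

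No new data are needed: the opioid-naive sample in Section 17.3 is defined by prior prescriptions and visit diagnosis, so it already includes visits without an opioid order. The cost is one more model, one table, one sentence on interpretation, and one additional secondary comparison.

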### 3.2 Secondary Endpoint(s)/Event(s)/Outcome(s):

#### Opioid-Naïve Population:

- 1) Whether a CDC-recommended non-opioid treatment is ordered in a primary care visit (e.g., referral to physical therapy, prescription of an NSAID, referral to pain clinic)
- 2) The length of opioid prescriptions
- 3) The MME of opioid prescriptions

#### Current opioid user Population:

- 1) Whether there was a partial reduction in the MME or prescription length of refill orders, versus a total opioid discontinuation
- 2) Whether there was an increase in the MME/day for current opioid users with at least 50 MME/day

#### All PCPs, including visits with opioid-naïve and current opioid-using patients:

- 1) The frequency with which PCPs check the PMP.
- 2) PCP satisfaction with decision support

#### Exploratory outcome:

For primary care appointments with someone currently receiving a “high risk” opioid, who did not get tapered, we will assess how frequently there is a documented clinical rationale for the decision to not taper, that is consistent with the CDC’s guidelines. This outcome is not linked to the experimental study arms.

## 4.0 Study Intervention(s)/Interaction(s)

### 4.1 Description:

The subjects of the study are primary care clinicians working in Fairview and in University of Minnesota Physicians. The interventions to be tested in this study are

sets of EHR clinical decision support tools (some of which are referred to as, “Best Practice Alerts”). These tools are very similar to many other EHR tools and alerts that clinicians encounter and use in their practice, and which are frequently adopted by health systems.

[figure not shown]
There are two sets of interventions to be tested. Both of these intervention sets use behavioral economics principles around “choice architecture.” One set includes a pair of EHR alerts – one that triggers for patients who are opioid-naïve (i.e., have not had an active opioid prescription in the past six months), and one that triggers for patients who are current opioid users. The other intervention is essentially the same for patients who are opioid-naïve or current opioid users.

These interventions will be delivered to all of the PCPs working in Fairview and UMP primary care clinics that are assigned to one of the intervention arms of the study (randomization arms are described in Section 5).

Detailed description of the Intervention Set A (choice architecture):

For the opioid-naïve group, the interventions will “fire” when a PCP initiates an opioid order within the EHR for a patient who has not had an opioid prescription within the past six months. The alert, shown in Exhibit 1a, provides guidance language about opioid prescribing and prompts the PCP to open the “SmartSet” to order non-opioid treatment alternatives. PCPs can choose to ignore this, but opening the SmartSet is the default option. When the SmartSet is opened, PCPs can choose to click on a variety of treatment order options, including both non-opioid pharmacological options and non-pharmacological options (e.g., referral to physical therapy or pain clinic). Clicking on a category expands the selections, and Exhibit 1b shows the SmartSet with the non-pharmacologic options expanded. The non-opioid treatment options were selected for the intervention based on the CDC’s chronic pain recommendations and the Fairview Opioid Network Team’s recommendations.

Exhibit 1a.

### Exhibit 1b.

[figure not shown]
Non-Opioid Alternatives SmartSet

- ▼ Medications
  - Anticonvulsants
  - Antidepressants
  - Anti-Inflammatories
  - Benzos / Hypnotics
  - Muscle Relaxants
  - Other Medications
- ▼ Non-pharmacological
  - ▼ Referrals
    - PRIMARY CARE INTEGRATED BEHAVIORAL HEALTH REFERRAL
    - PSYCHOLOGY REFERRAL
    - PHYSICAL THERAPY REFERRAL
    - MASSAGE THERAPY REFERRAL
    - PHYSIATRY REFERRAL
    - MHEALTH PAIN AND INTERVENTIONAL CLINIC REFERRAL
    - BEHAVIORAL / SPIRITUAL HEALTH (UMP ONLY)
- ▼ Additional Order Set Orders
  - 🔍 Search

You can search for an order by typing in the header of this section.

For the current-opioid user group, the interventions will “fire” when a refill order for an opioid is initiated or a new opioid order is initiated for a patient currently receiving an opioid. The alert, shown in Exhibit 2, prompts PCPs to consider tapering the patient’s opioid. The alert also displays the MME of the patient’s current opioid prescription and automatically calculates what a 10% reduction in MME relative to the current prescription would be. The alert contains options to either cancel the refill order, or to continue with the order.

[figure not shown]
